**Study title:**

Comparative safety and effectiveness of warfarin, dabigatran, and rivaroxaban among Japanese patients with non-valvular atrial fibrillation (NVAF) and concomitant coronary artery disease (CAD)

**EU PAS Register® number:** EUPAS41345

# BOEHRINGER INGELHEIM Group of Companies

## NIS Protocol

### BI Study Number 1160-0308

Page 33 of 46

c37044336-01

Proprietary confidential information © 2021 Boehringer Ingelheim International GmbH or one or more of its affiliated companies

**Study reference number (if applicable): 1160-0308**

Section 1: Milestones	Yes	No	N/A	Section Number
1.1 Does the protocol specify timelines for				
1.1.1 Start of data collection 				6.0
1.1.2 End of data collection 				6.0
1.1.3 Progress report(s)				
1.1.4 Interim report(s)				6.0
1.1.5 Registration in the EU PAS Register®				
1.1.6 Final report of study results.				6.0

Comments:

Section 2: Research question	Yes	No	N/A	Section Number
2.1 Does the formulation of the research question and objectives clearly explain:				
2.1.1 Why the study is conducted? (e.g. to address an important public health concern, a risk identified in the risk management plan, an emerging safety issue)				7.0
2.1.2 The objective(s) of the study?				8.0
2.1.3 The target population? (i.e. population or subgroup to whom the study results are intended to be generalised)				9.2.2
2.1.4 Which hypothesis(-es) is (are) to be tested?				8.0
2.1.5 If applicable, that there is no a priori hypothesis?				8.0

Comments:

Section 3: Study design	Yes	No	N/A	Section Number
3.1 Is the study design described? (e.g. cohort, case-control, cross-sectional, other design)				9.1
3.2 Does the protocol specify whether the study is based on primary, secondary or combined data collection?				9.1
3.3 Does the protocol specify measures of occurrence? (e.g., rate, risk, prevalence)				9.3.2

 Date from which information on the first study is first recorded in the study dataset or, in the case of secondary use of data, the date from which data extraction starts.

 Date from which the analytical dataset is completely available.

# BOEHRINGER INGELHEIM Group of Companies

## NIS Protocol

### BI Study Number 1160-0308

Page 34 of 46

c37044336-01

Proprietary confidential information © 2021 Boehringer Ingelheim International GmbH or one or more of its affiliated companies

Section 3: Study design	Yes	No	N/A	Section Number
3.4 Does the protocol specify measure(s) of association? (e.g. risk, odds ratio, excess risk, rate ratio, hazard ratio, risk/rate difference, number needed to harm (NNH))				9.7
3.5 Does the protocol describe the approach for the collection and reporting of adverse events/adverse reactions? (e.g. adverse events that will not be collected in case of primary data collection)				11.0

Comments:

Section 4: Source and study populations	Yes	No	N/A	Section Number
4.1 Is the source population described?				9.4
4.2 Is the planned study population defined in terms of:				
4.2.1 Study time period				9.2.2
4.2.2 Age and sex				9.2.2
4.2.3 Country of origin				9.2.2
4.2.4 Disease/indication				9.2.2
4.2.5 Duration of follow-up				9.2.2
4.3 Does the protocol define how the study population will be sampled from the source population? (e.g. event or inclusion/exclusion criteria)				9.2.2

Comments:

Section 5: Exposure definition and measurement	Yes	No	N/A	Section Number
5.1 Does the protocol describe how the study exposure is defined and measured? (e.g. operational details for defining and categorising exposure, measurement of dose and duration of drug exposure)				9.3.1
5.2 Does the protocol address the validity of the exposure measurement? (e.g. precision, accuracy, use of validation sub-study)				
5.3 Is exposure categorised according to time windows?				
5.4 Is intensity of exposure addressed? (e.g. dose, duration)				9.3.1
5.5 Is exposure categorised based on biological mechanism of action and taking into account the pharmacokinetics and pharmacodynamics of the drug?				

**BOEHRINGER INGELHEIM Group of Companies****NIS Protocol****BI Study Number 1160-0308**

Page 35 of 46

**c37044336-01**

Proprietary confidential information © 2021 Boehringer Ingelheim International GmbH or one or more of its affiliated companies

Section 5: Exposure definition and measurement	Yes	No	N/A	Section Number
5.6 Is (are) (an) appropriate comparator(s) identified?				9.1

Comments:

Section 6: Outcome definition and measurement	Yes	No	N/A	Section Number
6.1 Does the protocol specify the primary and secondary (if applicable) outcome(s) to be investigated?				9.3.2
6.2 Does the protocol describe how the outcomes are defined and measured?				9.3.2
6.3 Does the protocol address the validity of outcome measurement? (e.g. precision, accuracy, sensitivity, specificity, positive predictive value, use of validation sub-study)				
6.4 Does the protocol describe specific outcomes relevant for Health Technology Assessment? (e.g. HRQoL, QALYs, DALYs, health care services utilisation, burden of disease or treatment, compliance, disease management)				

Comments:

Section 7: Bias	Yes	No	N/A	Section Number
7.1 Does the protocol address ways to measure confounding? (e.g. confounding by indication)				9.7.1
7.2 Does the protocol address selection bias? (e.g. healthy user/adherer bias)				
7.3 Does the protocol address information bias? (e.g. misclassification of exposure and outcomes, time-related bias)				9.8

Comments:

Section 8: Effect measure modification	Yes	No	N/A	Section Number
8.1 Does the protocol address effect modifiers? (e.g. collection of data on known effect modifiers, subgroup analyses, anticipated direction of effect)				9.7.2

Comments:

# BOEHRINGER INGELHEIM Group of Companies

## NIS Protocol

### BI Study Number 1160-0308

Page 36 of 46

c37044336-01

Proprietary confidential information © 2021 Boehringer Ingelheim International GmbH or one or more of its affiliated companies

Section 9: Data sources	Yes	No	N/A	Section Number
9.1 Does the protocol describe the data source(s) used in the study for the ascertainment of:				
9.1.1 Exposure? (e.g. pharmacy dispensing, general practice prescribing, claims data, self-report, face-to-face interview)				9.4
9.1.2 Outcomes? (e.g. clinical records, laboratory markers or values, claims data, self-report, patient interview including scales and questionnaires, vital statistics)				9.4
9.1.3 Covariates and other characteristics?				9.4
9.2 Does the protocol describe the information available from the data source(s) on:				
9.2.1 Exposure? (e.g. date of dispensing, drug quantity, dose, number of days of supply prescription, daily dosage, prescriber)				9.3.1
9.2.2 Outcomes? (e.g. date of occurrence, multiple event, severity measures related to event)				9.3.2
9.2.3 Covariates and other characteristics? (e.g. age, sex, clinical and drug use history, co-morbidity, co-medications, lifestyle)				9.3.3
9.3 Is a coding system described for:				
9.3.1 Exposure? (e.g. WHO Drug Dictionary, Anatomical Therapeutic Chemical (ATC) Classification System)				9.3.1
9.3.2 Outcomes? (e.g. International Classification of Diseases (ICD), Medical Dictionary for Regulatory Activities (MedDRA))				9.3.2
9.3.3 Covariates and other characteristics?				9.3.3
9.4 Is a linkage method between data sources described? (e.g. based on a unique identifier or other)				9.4

Comments:

--

Section 10: Analysis plan	Yes	No	N/A	Section Number
10.1 Are the statistical methods and the reason for their choice described?				9.7
10.2 Is study size and/or statistical precision estimated?				9.5
10.3 Are descriptive analyses included?				9.7
10.4 Are stratified analyses included?				
10.5 Does the plan describe methods for analytic control of confounding?				9.7
10.6 Does the plan describe methods for analytic control of outcome misclassification?				

**BOEHRINGER INGELHEIM Group of Companies****NIS Protocol****BI Study Number 1160-0308**

Page 37 of 46

**c37044336-01**

Proprietary confidential information © 2021 Boehringer Ingelheim International GmbH or one or more of its affiliated companies

Section 10: Analysis plan	Yes	No	N/A	Section Number
10.7 Does the plan describe methods for handling missing data?				
10.8 Are relevant sensitivity analyses described?				9.7.2

Comments:

--

Section 11: Data management and quality control	Yes	No	N/A	Section Number
11.1 Does the protocol provide information on data storage? (e.g. software and IT environment, database maintenance and anti-fraud protection, archiving)				9.6
11.2 Are methods of quality assurance described?				9.10.1
11.3 Is there a system in place for independent review of study results?				

Comments:

--

Section 12: Limitations	Yes	No	N/A	Section Number
12.1 Does the protocol discuss the impact on the study results of: 12.1.1 Selection bias? 12.1.2 Information bias? 12.1.3 Residual/unmeasured confounding? (e.g. anticipated direction and magnitude of such biases, validation sub-study, use of validation and external data, analytical methods).	  	  	  	9.9 9.9 9.9
12.2 Does the protocol discuss study feasibility? (e.g. study size, anticipated exposure uptake, duration of follow-up in a cohort study, patient recruitment, precision of the estimates)				9.5

Comments:

--

Section 13: Ethical/data protection issues	Yes	No	N/A	Section Number
13.1 Have requirements of Ethics Committee/ Institutional Review Board been described?				10.1
13.2 Has any outcome of an ethical review procedure been addressed?				
13.3 Have data protection requirements been described?				10.2

**BOEHRINGER INGELHEIM Group of Companies****NIS Protocol****BI Study Number 1160-0308**

Page 38 of 46

c37044336-01

Proprietary confidential information © 2021 Boehringer Ingelheim International GmbH or one or more of its affiliated companies

Comments:

--

Section 14: Amendments and deviations	Yes	No	N/A	Section Number
14.1 Does the protocol include a section to document amendments and deviations?				5.0

Comments:

--

Section 15: Plans for communication of study results	Yes	No	N/A	Section Number
15.1 Are plans described for communicating study results (e.g. to regulatory authorities)?				12.0
15.2 Are plans described for disseminating study results externally, including publication?				12.0

Comments:

--

Name of the main author of the protocol: [REDACTED]Date: *2021/11/15*Signature: [REDACTED]**ANNEX 3. TABLE SHELLS**

Note: Table 1, Table 2a, and Table 3 are shown here to exemplify; please find the complete table shells in the attached excel file below:

Safety comparisons betw

Table 1. Patient Flow Diagram

	Excluded	Total
Total number of patients MDV database 2008-04-01 - 2020-12-31		
Total number of patients MDV database in study period 2011-04-01 - 2020-12-31		
Patients prescribed with Dabigatran, or Rivaroxaban or Warfarin		

# BOEHRINGER INGELHEIM Group of Companies

**NIS Protocol**

**BI Study Number 1160-0308**

Page 39 of 46

**c37044336-01**

Proprietary confidential information © 2021 Boehringer Ingelheim International GmbH or one or more of its affiliated companies

Patients older than 18 year old at drug index date		
Have 1y look-back prior drug index date		
New user of Dabigatran or Rivaroxaban or Warfarin		
Have at least 1 diagnosis of NVAF during the look-back period prior to or on the index date		
Have at least 1 diagnosis of CAD during the look-back period prior to or on the index date		
Excluded because of Diagnosis of end-stage renal disease, or undergo hemodialysis, or experience pregnancy during the study period		
Excluded because of Initiation of warfarin, dabigatran, rivaroxaban due to valvular AF, AF associated with mechanical valve malfunction or mechanical complication of heart valve prosthesis, or rheumatic AF		
Excluded because of Prescription with more than 1 OAC on the index date		
Final cohort	-	
Warfarin	-	
Dabigatran	-	
Rivaroxaban	-	

Table 2a. Baseline Characteristics Comparisons – Dabigatran vs. Warfarin

Variable	Overall			s-IPTWAdjusted			PS-matched		
	Da big atr an	Warfari n	Abs. Std. Dif	Dabigatra n	Wa rfar in	Abs.St d.Dif	Dabig atran	Warf arin	Abs.St d.Dif
Age									
...mean (sd)									
...median [IQR]									
...Min-Max									
Gender									
...1 - Male; n (%)									
...2 - Female; n (%)									

**BOEHRINGER INGELHEIM Group of Companies****NIS Protocol****BI Study Number 1160-0308**

Page 40 of 46

**c37044336-01**

Proprietary confidential information © 2021 Boehringer Ingelheim International GmbH or one or more of its affiliated companies

CHA2DS2-VASc score									
...mean (sd)									
...median [IQR]									
...Min-Max									
HAS-BLED score									
...mean(sd)									
...median[IQR ]									
...Min-Max									
Heart failure; n (%)									
Peripheral arterial disorder; n (%)									
Hypertension; n (%)									
Diabetes; n (%)									
Prior stroke/transient ischemic attack (TIA)/SE; n (%)									
Myocardial infarction; n (%)									
Acute Coronary Syndrome; n (%)									
Unstable angina; n (%)									
Bleeding history; n (%)									

**BOEHRINGER INGELHEIM Group of Companies****NIS Protocol****BI Study Number 1160-0308**

Page 41 of 46

**c37044336-01**

Proprietary confidential information © 2021 Boehringer Ingelheim International GmbH or one or more of its affiliated companies

Renal dysfunction; n (%)									
Hepatic dysfunction; n (%)									
Cancers; n (%)									
Peptic ulcer disease; n (%)									
Cerebrovascular disease; n (%)									
Obesity; n (%)									
Anti-platelet drugs (include aspirin, clopidogrel, ticagrelor, prasugrel); n (%)									
The number of anti-platelet drugs per prescription (single antiplatelet, dual antiplatelet, none)									
single antiplatelet; n (%)									
dual antiplatelet; n (%)									
none; n (%)									
Antiplatelet use duration									

**BOEHRINGER INGELHEIM Group of Companies****NIS Protocol****BI Study Number 1160-0308**

Page 42 of 46

**c37044336-01**

Proprietary confidential information © 2021 Boehringer Ingelheim International GmbH or one or more of its affiliated companies

Single antiplatelet use: 6 months to 1 year; n (%)									
Single antiplatelet use: 1 month to 6 months; n (%)									
Single antiplatelet use: <1 month; n (%)									
Dual antiplatelet use: 6 months to 1 year; n (%)									
Dual antiplatelet use: 1 month to 6 months; n (%)									
Dual antiplatelet use: <1 month; n (%)									
None; n (%)									
Nonsteroidal anti-inflammatory drugs; n (%)									
Gastric secretion inhibitors; n (%)									
Statins; n (%)									

# BOEHRINGER INGELHEIM Group of Companies

NIS Protocol

BI Study Number 1160-0308

Page 43 of 46

c37044336-01

Proprietary confidential information © 2021 Boehringer Ingelheim International GmbH or one or more of its affiliated companies

Heparins; n (%)								
Proton pump inhibitor; n (%)								
Antihypertensive drugs; n (%)								
Cardiovascular procedures; n (%)								
Ablation procedures; n (%)								
Percutaneous Coronary Intervention or Coronary Artery Bypass Grafting; n (%)								

Table 3. Rates and Risks of Fatal/Non-fatal Major Bleeding

	Comparison 1		Comparison 2		Comparison 3*	
	Dabigatran	Warfarin	Rivaroxaban	Warfarin	Dabigatran	Rivaroxaban
Rate						
Overall						
Number of patients						
Number of events						
Number of person-years						
Incidence Rate per 1,000 person-years (95% CI)						
Incidence Proportion (n (%))						
s-IPTW adjusted						

**BOEHRINGER INGELHEIM Group of Companies****NIS Protocol****BI Study Number 1160-0308**

Page 44 of 46

**c37044336-01**

Proprietary confidential information © 2021 Boehringer Ingelheim International GmbH or one or more of its affiliated companies

Number of patients						
Number of events						
Number of person-years						
Incidence Rate per 1,000 person-years (95% CI)						
Incidence Proportion (n (%))						
PS-matched						
Number of patients						
Number of events						
Number of person-years						
Incidence Rate per 1,000 person-years (95% CI)						
Incidence Proportion (n (%))						
Hazard ratios						
s-IPTWAdjusted Hazard Ratio (95% CI)						
PS Matched Hazard Ratio (95% CI)						

\*Note: comparison 3 will be conducted if sample size is sufficient (see section 9.5 of protocol)

**BOEHRINGER INGELHEIM Group of Companies****NIS Protocol****BI Study Number 1160-0308**

Page 46 of 46

**2. LIST OF ABBREVIATIONS**

BI	Boehringer Ingelheim
CI	Confidence Interval
IQR	Interquartile range
NIS	Non-interventional study
SEAP	Statistical and epidemiological analysis plan
DMRP	Data management and review plan
AE	Adverse Event
AF	Atrial Fibrillation
ASD	Absolute Standardized Difference
CA	Competent Authority
CAD	Coronary Artery Disease
CCDS	Company Core Data Sheet
CHA2DS2-	Congestive heart failure, Hypertension, Age $\geq 75$ years, Diabetes mellitus, Stroke, Vascular disease, Age 65-74 years, Sex category (female)
VASc	mellitus, Stroke, Vascular disease, Age 65-74 years, Sex category (female)
CI	Confidence Interval
CML	Local Clinical Monitor
CRA	Clinical Research Associate
CRF	Case Report Form
CTP	Clinical Trial Protocol
DMRP	Data Management and Review Plan
DCP	Diagnosis Procedure Combination
eCRF	Electronic Case Report Form
ENCePP	European Network of Centres for Pharmacoepidemiology and Pharmacovigilance
EMA	European Medicines Agency
ESC	European Society of Cardiology
FDA	Food and Drug Administration
GCP	Good Clinical Practice
GEP	Good Epidemiological Practice
GI	Gastrointestinal
GPP	Good Pharmacoepidemiology Practice
GVP	Good Pharmacovigilance Practices
HAS-BLED	Hypertension, Abnormal renal/liver function, Stroke, Bleeding history or predisposition, Labile INR, Elderly ( $>65$ years), Drugs/alcohol concomitantly
HR	Hazard Ratio
IB	Investigator's Brochure
ICD-10	The 10 th Revision of the International Classification of Diseases
ICH	Intracranial Hemorrhage
ID	Identification Number

IEC	Independent Ethics Committee
IPTW	Inverse Probability of Treatment Weighting
IRB	Institutional Review Board
MAH	Marketing Authorization Holder
[REDACTED]	[REDACTED]
MedDRA	Medical Dictionary for Regulatory Activities
MI	Myocardial Infarction
NIS	Non-Interventional Study
NOAC	Non-vitamin K Oral Anticoagulant
NVAF	Non-valvular Atrial Fibrillation
SE	Systemic Embolism
VAF	Valvular Atrial Fibrillation
ESRD	End-stage renal disease
OAC	Oral Anticoagulation

### **4. PURPOSE AND SCOPE**

SEAP reviewers are expected to be familiar with the NIS protocol entitled “Comparative safety and effectiveness of warfarin, dabigatran, and rivaroxaban among Japanese patients with non-valvular atrial fibrillation (NVAF) and concomitant coronary artery disease (CAD)” version 1.0 dated 15 November 2021 unless otherwise stated.

# **BOEHRINGER INGELHEIM Group of Companies**

## **Statistical and Epidemiological Analysis Plan (SEAP) for Non-Interventional Studies (NIS)**

c38948754-01

Page 6 of 32

---

Proprietary confidential information © 2022 Boehringer Ingelheim International GmbH or one or more of its affiliated companies

The SEAP addresses the details of the implementation of this study. In the SEAP, you can find the detailed definitions on how to identify each of the index medication cohorts, detailed data analysis plan such as the inverse probability of treatment weighting (IPTW), propensity score matching and main analysis plan.

**5. AMENDMENTS AND UPDATES**

None

**6. RESEARCH QUESTION AND OBJECTIVE**

This non-interventional cohort study using data from large Japan clinical database to access the safety and effectiveness of oral anticoagulants among patients with non-valvular atrial fibrillation (NVAF) and concomitant coronary artery disease (CAD).

**Primary objective:**

To compare the risk of major bleeding between dabigatran and warfarin, and between rivaroxaban and warfarin, among Japanese NVAF patients with concomitant CAD.

**Secondary objective:**

To compare the net clinical benefits of dabigatran vs. warfarin, and rivaroxaban vs. warfarin, among Japanese NVAF patients with concomitant CAD. The net clinical benefits are defined as free of composite outcome of stroke/SE/MI/all-cause mortality (inpatient)/major bleeding/major GI bleeding (hospitalization due to GI bleeding)/ICH.

**Further objective:**

If the required sample size can be fulfilled and the baseline characteristics are balanced between dabigatran and rivaroxaban groups after IPTW adjustment, to compare the safety and net clinical benefits of dabigatran vs rivaroxaban among Japanese NVAF patients with concomitant CAD.

## **7. RESEARCH METHODS**

### **7.1 STUDY DESIGN**

This study will be a non-interventional cohort study based on existing data, the [REDACTED] [REDACTED] database. It contains comprehensive medical record data, blood test result data and insurance claims data. Patients meeting the in/exclusion criteria will be selected and will be defined as 3 patient groups:

Group 1: new users of warfarin

Group 2: new users of dabigatran

Group 3: new users of rivaroxaban

Comparative analyses of the study will follow a two-step approach. In the first step, the primary and secondary outcomes, as well as baseline characteristics, will be compared between Group 1&2 and Group 1&3, respectively.

The second step will utilize the estimated results from step one, which are HRs of major bleeding events between Group 1&2 and between Group 1&3 among NVAF patients with concomitant CAD, to carry out a more accurate sample size calculation to compare dabigatran versus rivaroxaban. If feasible, comparisons will be made on the same outcomes as in step one.

### **7.2 SETTING**

**Study Period:** the entire time period that includes the look-back period, the cohort entry date (drug index date), and follow-up period for the study population. The study period will be from April 18th, 2011 (start of data collection) to December 31st, 2020 (end of data collection).

**Patient Selection Period:** the time period for which patients are eligible to enter the cohort, which is from April 18th, 2012 to December 31st, 2020.

**Cohort Entry Date:** The drug index date, defined as the first date of prescription for dabigatran, rivaroxaban, or warfarin during the patient selection period.

**Look-back Period:** the 365-day period that ends 1 day prior to the cohort entry date. The earliest start date of the look-back period is April 18th, 2011.

**Loss of follow-up:** the last data point available in the database during the study period.

#### **7.2.1 Follow up period**

The follow up period starts from cohort entry date (first prescription of the drug of interest) and ends at the earliest date of the following dates:

- Discontinuation date of index OAC.

Proprietary confidential information © 2022 Boehringer Ingelheim International GmbH or one or more of its affiliated companies

Discontinuation of the index OAC, defined as a continuous gap of 45 days or more between the expected refill date and the actual refill date. The discontinuation date is defined as 45 days after the expected refill date. The codes for index OAC are listed in [Annex 1](#).

- Date of switching to another OAC.  
If the index OAC is discontinued, the date of switching to another OAC was the first prescription date of another OAC within 45 days of the expected refill date of the index OAC. The codes of another OAC are the codes in [Annex 1](#) excluding codes of the index OAC.
- Loss of follow-up date.  
The date of the last inpatient/outpatient encounter during period starting from index OAC date and ending on December 31st, 2020.
- Date of the first occurrence of outcomes of interest (for primary outcome: major bleeding; for secondary outcome: the onset of the first occurring component event; for further outcomes: the respective onset of component events) during period starting from index OAC date and ending on December 31st, 2020.
- Date of death during period starting from index OAC date and ending on December 31st, 2020.
- End of study period date (December 31st, 2020).

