## **9.2 SETTING**

**Study Period:** the entire time period that includes the look-back period, the cohort entry date (drug index date), and follow-up period for the study population. The study period will be from April 18th, 2011 (start of data collection) to December 31st, 2020 (end of data collection).

**Patient Selection Period:** the time period for which patients are eligible to enter the cohort, which is from April 18th, 2012 to December 31st, 2020.

**Cohort Entry Date:** The drug index date, defined as the first date of prescription for dabigatran, rivaroxaban, or warfarin during the patient selection period.

**Look-back Period:** the 365-day period that ends 1 day prior to the cohort entry date. The earliest start date of the look-back period is April 18th, 2011.

**Loss of follow-up:** the last data point available in the database during the study period.

**Follow-Up Period:** the period starting from the cohort entry date (first prescription of the drug of interest) and ending at the earliest occurrence of the following:

- Discontinuation of the index OAC, defined as a continuous gap of 45 days or more between the expected refill date and the actual refill date (discontinuation date defined as 45 days after the expected refill date)
- Switching to another OAC, if the index OAC is discontinued and another OAC is started within 45 days of the expected refill date of the index OAC
- Loss of follow-up
- Occurrence of outcomes of interest (for primary outcome: major bleeding; for secondary outcome: the onset of the first occurring component event; for further outcomes: the respective onset of component events)
- Death (except for analyses for the composite outcome and all-cause mortality as a component outcome)
- End of study period

The notion of enrollment is not defined in [REDACTED]. Therefore, a proxy enrolment criterion defined as start of enrolment = date of first inpatient/outpatient encounter; end of enrolment = date of last inpatient/outpatient encounter will be used. "Enrolment" herein will refer to this proxy enrolment measure. For entry into the study population, patients will be required to have had at least 365 days of enrollment prior to the cohort entry date.

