## **9.5 STUDY SIZE**

During the period from April 2011 to December 2020, there are roughly 17000, 11000, and 4000 NVAF adult patients with a medical history of CAD being respectively treated with either warfarin, rivaroxaban or dabigatran as the first OAC (defined as no history of OAC usage during the 12-month look-back period) within the [REDACTED] database.

According to a published paper based on the [REDACTED] database, the mean (standard deviation, SD) treatment duration of different drugs among new user groups ranged from 265 (263.8) to 868 (725) days, with the dabigatran group exposed to the treatment the longest [P20-03503]. According to the same article, the major bleeding rate for AF patients is 1.5 per 100 patient-years. In comparison, AF patients with concomitant CAD are more likely to fall under high or medium/high risk categories of the HAS-BLED score, a predictor of bleeding complications among AF patients, thus increasing the event rate for major bleeding about 2-3 times [P09-11669], [R11-4223]. Therefore, the major bleeding rate is assumed to be rather 3-4.5 per 100 patient-years among Japanese AF+CAD patients in the [REDACTED] database.

Furthermore, previous analysis concluded substantial superiority of dabigatran (HR=0.66, 95% CI 0.529-0.825) and rivaroxaban (HR=0.74, 95% CI 0.618-0.879) over warfarin in major bleeding among AF patients [P09-11669], [R11-4223]. The comparative rates of major bleeding between individual NOAC- and warfarin- treated patients should follow a similar trend among NVAF patients with concomitant CAD.

For dabigatran vs. warfarin, if the HR is assumed to be 0.66 and the average exposure time to be 1 year per patient, an event rate of 3 per 100 patient-years with 80% power will require a total sample size of 6050 patients and 3025 patients for each arm; an event rate of 4.5 per 100 patient-years will require a total sample size of 4040 patients and 2020 patients for each arm. To be conservative, the lower bound is selected and therefore each arm needs around 3025 patients.

Similarly, assuming the HR of rivaroxaban vs. warfarin is 0.74 and the average exposure time to be 1 year per patient, the lower-bound event rate of 3 per 100 patient-years with 80% power will require a total sample size of 9690 patients and 4845 patients for each arm.

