### **8.2 OUTCOMES**

#### **8.2.1 Primary outcomes**

Operational definition of fatal or non-fatal major bleeding is the first new confirmed diagnosis of

- blood transfusion (inpatient or outpatient)  
OR
- bleeding of inpatient (non-DPC hospital)  
OR
- bleeding of inpatient (DPC hospital) with “disease name behind this hospitalization” (“dpcdiseasesegment”=21)

during the follow up period. The ICD-10 diagnosis codes of blood transfusion and bleeding are in [Annex 3](#).

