Proprietary confidential information © 2022 Boehringer Ingelheim International GmbH or one or more of its affiliated companies

The baseline demographics, risk factors, and clinical characteristics will be compared between the treatment groups (dabigatran vs warfarin, rivaroxaban vs warfarin, dabigatran vs rivaroxaban) using the absolute standardized difference (ASD) pre- and post- s-IPTW to assess the balance of these confounders. A covariate will be considered well balanced if the ASD is below 0.1.

A Cox proportional hazard regression model with s-IPTW will be used to estimate adjusted hazard ratios (aHRs) of treatments (dabigatran vs warfarin, rivaroxaban vs warfarin) and their 95% CIs on primary, secondary, and further outcomes. The treatment membership is the independent variable in the model. A patient will be censored if discontinuation of the index OAC or switching to another OAC or death or loss to follow-up occurred before outcome event. If substantial covariate imbalance between treatment group is noted assessed by a standardized difference  $>0.1$ , then the Cox proportional hazard model will be further adjusted by including covariates that are out of balance in the model. A robust sandwich variance estimation of the treatment effect estimates will be used to account for the fact that the pseudo-population size is inflated or deflated relative to the original population and that weights are estimated [\[P21-02302\]](#).

A sensitivity analysis will be performed by restricting the follow-up period to 3 years for Cox regression models on primary and secondary outcomes.

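### Ending follow-up at the last hospital encounter makes censoring depend on the outcome: on-drug time after the last routine visit counts only when a captured event occurs, which inflates rates and can bias the HRs either way

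*SAP*

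**What the plan says.** Under SAP 7.2.1, follow-up "ends at the earliest date of the following dates": discontinuation, switch, loss to follow-up, outcome, death or end of study. Two of these matter here.

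- Loss to follow-up: "The date of the last inpatient/outpatient encounter during period starting from index OAC date and ending on December 31st, 2020".
- Discontinuation: "The discontinuation date is defined as 45 days after the expected refill date".

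Protocol 9.2 gives the reason for the first. The database has no enrolment concept, so encounters stand in for it: "end of enrolment = date of last inpatient/outpatient encounter will be used".

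The primary outcome (SAP 8.2.1) is built from hospital contacts, for example "blood transfusion (inpatient or outpatient" and "bleeding of inpatient (non-DPC hospital". The composite (SAP 8.2.2) adds stroke, systemic embolism, MI and inpatient death. SAP 11.1 censors a patient when, among other things, "loss to follow-up occurred before outcome event".

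Protocol 9.5 cites mean treatment durations of 265 to 868 days across drugs, "with the dabigatran group exposed to the treatment the longest".

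**The concern.** The discontinuation date always falls after the last prescription. A patient with no encounter after that prescription is therefore cut at it, and the dispensed supply plus 45 days is discarded. If the same patient bleeds in that window and is treated at a database hospital, the bleed becomes an encounter. The loss-to-follow-up date moves to the bleed or later, and both the event and the days before it count. Whether the window enters the analysis thus depends on the outcome.

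Two groups feel this most. Patients with one prescription and no further visit have zero follow-up unless they have an event. Patients still on drug in December 2020 are cut at their last visit and not at 31 December, unless an event brings them back.

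The rates in Table 3, the composite and the Cox models all inherit the rule. The sensitivity analyses that can be read (propensity-score matching and the 3-year cap) leave it in place.

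**Working it through.** **1. How the dates order themselves.** Illustration: last fill on day 0 with 30 days' supply, so discontinuation is day 30 + 45 = 75.

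| Patient | Follow-up ends | Counted after last fill |
|---|---|---|
| No later encounter, no event | day 0 | nothing; 75 days dropped |
| Same, but a bleed is admitted to a database hospital on day 20 | day 20 (outcome) | 20 days and the event |
| No event, last visit on day 20 | day 20 | 20 days; 55 dropped |
| No event, a visit on or after day 75 | day 75 | all 75 days |

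**2. Effect on a rate.** The plan states no figure for this rule, so there is none to reproduce.

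- V: mean days from index to last routine visit
- S: days' supply; g = S + 45
- f: share with no encounter after the last fill unless they have an event
- c: probability that such a late event is seen in the database
- K = V + (1 − f)g: mean days kept without an event

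At a low constant hazard:

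- current rule, observed/true rate = (K + cfg)/K, never below 1
- everyone followed to refill + 45 days, observed/true rate = (K + cfg)/(V + g), never above 1

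The 265 and 868 days come from protocol 9.5 and are assumed here to be V in the two arms. S, f and c are not in the documents. With f = c = 0.5:

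| S | V | K | cfg | Current rule | Extended rule |
|---|---|---|---|---|---|
| 30 | 265 | 302.5 | 18.75 | 321.25/302.5 = 1.062 | 321.25/340 = 0.945 |
| 30 | 868 | 905.5 | 18.75 | 924.25/905.5 = 1.021 | 924.25/943 = 0.980 |
| 90 | 265 | 332.5 | 33.75 | 366.25/332.5 = 1.102 | 366.25/400 = 0.916 |
| 90 | 868 | 935.5 | 33.75 | 969.25/935.5 = 1.036 | 969.25/1003 = 0.966 |

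Ratio of the longer- to the shorter-duration arm when the true ratio is 1.0:

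- current rule: 1.021/1.062 = 0.96 (S = 30); 1.036/1.102 = 0.94 (S = 90)
- extended rule: 0.980/0.945 = 1.04; 0.966/0.916 = 1.05 to 1.06

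A simulation of the rule gave 0.96 and 0.93 (current) and 1.04 and 1.07 (extended). The formula credits everyone who does not leave with the full window, so it does not model the third patient in step 1.

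Limits of c, with S = 30 and f = 0.5:

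- c = 0: the current rule is unbiased. The extended rule gives (905.5/943)/(302.5/340) = 0.960/0.890 = 1.08.
- c = 1: the extended rule is unbiased. The current rule gives (943/905.5)/(340/302.5) = 1.041/1.124 = 0.93.

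**3. Direction of HR bias.** If V, S, f and c are equal in both arms, the factor is the same and cancels. Cox simulations with equal arms and full capture returned 0.995 to 1.008 for a true 1.00.

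Now let supply differ. Take full capture, f = 0.5 and T = 365 on-drug days to the discontinuation date in both arms. The factor is T/(T − fg):

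- S = 30: 365/327.5 = 1.115
- S = 60: 365/312.5 = 1.168
- S = 90: 365/297.5 = 1.227

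With 30 days' supply on warfarin and 60 or 90 on the NOAC, a true 1.00 becomes 1.168/1.115 = 1.05 or 1.227/1.115 = 1.10, against the NOAC. Simulation agrees (1.05 and 1.10).

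**4. Scale against the planned precision.** Schoenfeld's formula at HR 0.66, two-sided 5% (assumed) and 80% power gives 4(1.960 + 0.842)²/(ln 0.66)² = 182 events, and 182/0.03 = 6067, against the protocol's 6050. The standard error of the log HR is 2/√182 = 0.148. A shift to 0.96 or 0.93 (0.041 or 0.073 on the log scale) is 0.28 or 0.49 of it.

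With the 4000 dabigatran and 17000 warfarin patients expected in protocol 9.5, one year each at 3 per 100 patient-years gives 630 events. The standard error is then about 1/√(630 × 0.19 × 0.81) = 0.10, and the shifts are about 0.4 and 0.7 of it.

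**The case against.** The encounter rule is a deliberate answer to a real problem. Without an enrolment concept, the last encounter is the last moment at which a patient is known to be observable. Protocol 9.9 says the database is not a closed system. A patient with no later visit may have moved to another provider, and following that patient for supply plus 45 days adds time in which events cannot be seen. This stands: step 2 shows that the extended rule errs the other way when capture is incomplete, so it should not simply replace the main analysis.

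The size is also unanchored. Supply, visit interval, the share leaving and capture are not in the documents, by arm or overall. The affected time is bounded by remaining supply plus 45 days for patients with no encounter on or after the discontinuation date.

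Two stronger readings are tempting and are not supported. A reader might infer that any later visit secures follow-up to refill + 45 days. Under an earliest-of rule, only a visit on or after that date does. A reader might also infer that the rule makes the longer-treated drug look safer. Protocol 9.5 says only that dabigatran had the longest treatment; it does not give 265 days to warfarin or rivaroxaban, and longer supply in one arm can reverse the direction.

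Finally, protocol 9.7.2 and SAP 11.2 are redacted, so a follow-up sensitivity analysis there cannot be ruled out. What the objection does not remove is the mechanism itself, which follows from the visible text.

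**Conclusion.** The concern holds as a matter of definition: under SAP 7.2.1, time after the last routine visit is kept or dropped according to whether a captured event occurs. Rates are inflated whenever c is above zero, by about 2% to 10% in the examples with f = c = 0.5. The HRs are unaffected if the arms are alike in duration, supply, visit interval, loss and capture. They are biased otherwise, in a direction the documents do not settle.

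For a true ratio of 1.0, the duration example gives about 0.93 to 0.96, and the supply example with full capture gives 1.05 to 1.10. These rest on assumed values for S, f and c and on assigning 265 and 868 days to the two arms. They show plausible size and are not estimates. The issue is moderate: worth settling before analysis because it touches the primary outcome, but no ground for discarding the current rule.

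**What to change.** Keep the existing definition and add to SAP 7.2.1 and 11.1 a pre-specified analysis of the primary and secondary outcomes. In it, every patient without a further refill is followed to the expected refill date plus 45 days, capped at 31 December 2020, whether or not a later encounter exists. Follow-up still ends earlier at switch, outcome or death.

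Report both definitions side by side. Under the assumptions of step 2 they bracket each arm's rate, and they bracketed the ratio in the examples. That is not guaranteed if capture differs by arm.

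Report by arm the number of patients with zero follow-up and the number cut at the last encounter before their discontinuation date, so that readers can judge whether the arms differ.

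The cost is SAP wording, one more derived end date and a second set of models; no new data are needed. The downside is that the added days include patients who moved to another provider and whose events are unseen, so the extended version may undercount events. State this next to the results.
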